## 6 STUDY ENDPOINTS

### 6.1 Pharmacokinetic endpoints

#### 6.1.1 Primary pharmacokinetic endpoint(s)

The primary endpoint is model-based exposure ( $AUC_{\tau,ss,combined}$ ) of selexipag and ACT-333679 corrected for their potency, determined during the 12-week up-titration period. It is compared to the model-based exposure for participants with PAH in GRIPHON. The GRIPHON population PK model will be used and updated based on the acquired pediatric PK data. The model will describe the body weight dependence of the dose-exposure relationship for pediatric participants with PAH [[Modeling and Simulation Report, Pediatric dose selection 2016](#)].

### 6.1.2 Secondary pharmacokinetic endpoints:

- Area under the plasma concentration-time curve over one dosing interval at steady state ( $AUC_{\tau,ss}$ ), maximum plasma concentration at steady state ( $C_{max,ss}$ ), and the time at which  $C_{max,ss}$  is observed ( $t_{max,ss}$ ) for selexipag and ACT-333679 based on non-compartmental analysis (NCA).
- Trough concentration at steady state ( $C_{trough,ss}$ ) on Day 15 / Visit 4, and at Week 4 / Visit 5 and Week 6 / Visit 6 for selexipag and ACT-333679.

### 6.2 Safety endpoints

- Treatment-emergent AEs (TEAEs) occurring up to EOT + 3 days.
- Treatment-emergent SAEs (TESAEs) occurring up to EOT + 3 days.
- AEs leading to permanent discontinuation of study drug.
- Treatment-emergent deaths (all causes) occurring up to EOT + 3 days.
- Treatment-emergent marked laboratory abnormalities (hematology and blood chemistry tests) over time occurring up to EOT + 3 days.
- Change from baseline in selected hematology and blood chemistry laboratory variables over time up to EOT + 3 days.
- Treatment-emergent ECG abnormalities over time occurring up to EOT + 3 days.
- Change from baseline in TSH over time up to EOT + 3 days.
- Change from baseline in vital signs (blood pressure, heart rate) over time up to EOT + 3 days.
- Change from baseline in height and body mass index over time up to EOT + 3 days.
- Change from baseline in sexual maturation (Tanner stage) over time up to EOT + 3 days.

### 6.3 Exploratory endpoints

- Change from Baseline/Enrollment up to each time point of assessment in modified New York Heart Association (NYHA) / WHO FC.
- Change from baseline up to each time point of assessment in exercise capacity as measured by 6MWD.
- Change from baseline in Panama FC up to each time point of assessment.
- Percent of baseline in plasma NT pro-BNP at each time point of assessment.

- Change from baseline to each time point assessment in Echo variables (imaging and Doppler evaluation):
  - Right ventricular systolic pressure.
  - Tricuspid annular plane systolic excursion.
  - Pulmonary artery acceleration time.
  - Left ventricular eccentricity index.
  - Right atrial area index (from apical 4 chamber view).
  - Tricuspid annular diameter (from apical 4 chamber view).
- Time to the first of the following disease progression events occurring between first study drug dose and EOT + 7 days:
  - Death (all causes)
  - Atrial septostomy or Potts' anastomosis, or registration on lung transplant list
  - Hospitalization due to worsening PAH§
  - Clinical worsening\* of PAH defined as:  
Need for, or initiation of new PAH-specific therapy# or i.v. diuretics or continuous oxygen use AND at least one of the following:
    - Worsening in WHO FC, or
    - New occurrence or worsening of syncope (in frequency or severity as per medical judgment), or
    - New occurrence or worsening of at least two PAH symptoms (i.e., shortness of breath/dyspnea, chest pain, cyanosis, dizziness/ near syncope, or fatigue), or
    - New occurrence or worsening of signs of right heart failure not responding to oral diuretics

§excluding hospitalizations that are elective, routine or clearly attributable to appearance/worsening of comorbidities (eg, pneumonia).

\*worsening from baseline.

#eg, ERA, PDE-5 inhibitor, prostanoids, prostacyclin receptor (IP receptor) agonist, soluble guanylate cyclase stimulator.

#### 6.4 Other endpoints

- Palatability of selexipag formulation at Day 1, Week 12, and EOT, assessed using a 5-point facial hedonic scale.

- Acceptability of selexipag formulation at Day 1, Week 12, and EOT, as assessed through a 3-point categorical scale as to whether the child swallowed the medication.

## 7 VISIT SCHEDULE AND STUDY ASSESSMENTS

### 7.1 Study visits

The study visits are listed in [Table 4](#) and [Table 5](#). For all visits, the participants must be seen on the designated day with an allowed visit window indicated in the tables. An EOT visit must be performed within 7 days of intake of the last dose of study treatment. A safety follow-up call should follow 30 days after this visit, and will be considered the EOS for an individual participant.

All assessments pertaining to a visit should be performed on the same day. If this is not possible, the visit may extend over more than 1 day within the allowed time window.

If study treatment is prematurely discontinued, the EOT visit must take place as soon as possible and no later than 7 days after the last dose of study treatment. A safety follow-up call should follow 30 days after this visit.

Participants who prematurely discontinue study treatment / study participation for any reason before contributing to PK sampling, or for whom PK samples are missing / have been mishandled, may be replaced.

#### 7.1.1 Screening/re-screening

Screening starts with the signature of the ICF. The date on which the first screening assessment is performed corresponds to the date of the Screening visit.

It is the responsibility of the investigator/delegate to obtain written informed consent from the parent(s)/LAR(s) of each participant participating in this study after adequate face-to-face explanation of the objectives, methods, and potential hazards of the study. The participant's parent(s)/LAR(s) who agree that their child will participate in the study and the investigator/delegate must sign the ICF (and, if applicable, the participant's assent form) prior to any study-related assessment or procedure.

Participants whose parent(s)/LAR(s) have already signed the ICF (and, if applicable, the participant's assent form) when the enrollment target has been met may still be enrolled.

It is permitted to re-screen participants once, if the reason for non-eligibility was transient (eg, abnormal laboratory test, insufficient wash-out period of a forbidden medication). If a participant is re-screened, only the safety laboratory assessments must be repeated. Re-consent is needed if the initial consent signature is more than 42 days old.

### 7.1.2 Unscheduled visits

Unscheduled visits can be performed for any reason including (but not limited to) safety issues, PAH worsening, and study drug dispensation. Depending on the reason for the unscheduled visit (eg, AE), appropriate assessments will be performed based on the judgment of the investigator and the results will be recorded in the eCRF.

If the reason for an unscheduled visit is suspected PAH worsening / PAH disease progression (eg, signs/symptoms denoting PAH worsening or deterioration of WHO FC [refer to Sections 7.2.2.1 and 7.2.2.2]), the investigator determines the main and contributing causes for worsening as per local practice, preferably including the following assessments (these are also recommended even if PAH progression is assessed at a scheduled visit and in case these assessments are not planned for that particular visit):

- Vital signs
- Concomitant medications (including contraceptives)
- PAH-related non-pharmacological intervention
- Signs/symptoms of PAH
- WHO FC and Panama FC
- Main and contributing cause(s) of worsening
- Central laboratory tests including plasma NT-proBNP
- Physical examination
- Echocardiography (central)

The onset date of worsening, the main and contributing cause(s) for worsening are recorded in the eCRF.

The event itself as well as contributing causes unrelated to PAH are reported as AE/SAE.

If RHCs are performed during the study for any medical reason, as judged by the investigator, these results should be recorded in the eCRF.

After an unscheduled visit, the regular scheduled study visits must continue according to the planned visit and assessment schedule [Table 4, Table 5].

**Table 4 Visit and assessment schedule until Week 16**

Period	Screening	Base-line/ Enrollment	Treatment													
			Up-titration												Maintenance	
Name	Screening visit / Visit 1	Visit 2	Visit 3 b or Tel	Visit 4	Tel. a W3	Visit 5	Tel. a W5	Visit 6	Tel. a W7	Tel. a W8	Tel. a W9	Tel. a W10	Tel. a W11	Visit 7	Tel. a W14	Visit 8
Time	≤ 42 days before Day 1	Day 1	Week 1 Day 5 1 / +2 d	Week 2 Day 15 ± 3 d	Week 3 Day 22 ± 3 d	Week 4 ± 3 d	Week 5 ± 3 d	Week 6 ± 3 d	Week 7 ± 3 d	Week 8 ± 3 d	Week 9 ± 3 d	Week 10 ± 3 d	Week 11 ± 3 d	Week 12 ± 3 d	Week 14 ± 3 d	Week 16 / M4 ± 3 d
Written informed consent	X															
Inclusion/exclusion criteria (incl. hemodynamics)	X															
Med. History incl. PAH diagnosis	X															
Previous/Concomitant medications	X	X				X		X						X		X
Mod. NYHA/WHO FC	X	X														X
Panama FC	X	X														X
PAH signs/symptoms	X	X														X
PAH-related non-pharmacological interventions			If applicable													
Physical examination	X l	X k				X k								X k		X k
Growth: Weight and height	X m	X												X		X m
Vital signs (blood pressure, heart rate)	X	X				X								X		X
ECG		X	X g			X								X g		X
Echo n		X														X
6MWD test h		X i														X

Pulmonary arterial hypertension

Protocol AC-065A203

Confidential

Amendment 7 Version 8

30 September 2021, page 81/154

Period	Screening	Base-line/ Enrollment	Treatment													
			Up-titration												Maintenance	
Name	Screening visit / Visit 1	Visit 2	Visit 3 b or Tel	Visit 4	Tel. a W3	Visit 5	Tel. a W5	Visit 6	Tel. a W7	Tel. a W8	Tel. a W9	Tel. a W10	Tel. a W11	Visit 7	Tel. a W14	Visit 8
Time	≤ 42 days before Day 1	Day 1	Week 1 Day 5 1 / + 2 d	Week 2 Day 15 ± 3 d	Week 3 Day 22 ± 3 d	Week 4 ± 3 d	Week 5 ± 3 d	Week 6 ± 3 d	Week 7 ± 3 d	Week 8 ± 3 d	Week 9 ± 3 d	Week 10 ± 3 d	Week 11 ± 3 d	Week 12 ± 3 d	Week 14 ± 3 d	Week 16 / M4 ± 3 d
Tanner stage	X															X
Childbearing potential	X	X	X	X		X		X			X			X		X
Pregnancy test (if appl.) e	X	X				X				X				X		X
Laboratory test, Hematology/Chemistry f	X	X				X								X		X
TSH		X				X								X		X
Thyroid antibodies		X	X when medically indicated													
T3 and T4			X when TSH is abnormal or when medically indicated													
Plasma NT pro-BNP		X														X
Palatability and acceptability of selexipag		X													X	
PK sampling			X b	X c		X c		X c							X d	
Study drug dispensing		X													X	X
First dose of study drug		X (p.m.)														
Dose titration			X	X	X	X	X	X	X	X	X	X	X	X	X j	
Drug accountability								X						X		X
(Serious) adverse events	X	X	X	X	X	X	X	X	X	X	X	X	X	X	X	X

- a. Tel. Scheduled telephone call.
  - b. PK samples will be taken at pre dose, 1, 2, 4, 6, 8 h and 12 h post morning dose of selexipag in the first 5 participants of Cohorts 1-3 (participant should have been at least 3 days on the same dose and mode of administration to reach steady state). The PK sample at 12 h post morning dose must be before the evening dose of selexipag. For the rest of the participants, a phone call will be done instead of a visit.
  - c. Trough morning PK samples to be collected from all participants prior to dose escalation at Visits 4, 5, and 6 (participant should have been on the same dose and mode of administration for at least 3 days to reach steady state).
  - d. For all participants of each cohort who did not provide the starting dose profiles: PK samples to be collected at pre dose, 1, 2, 4, 6, 8 h and 12 h post morning dose of selexipag at highest tolerated dose at Week 12 (at least 3 days on the same dose level and mode of administration to reach steady state). The PK sample of 12 h must be before the evening dose of selexipag.
  - e. Serum pregnancy test to be performed at screening and urine pregnancy tests every 4 weeks until 30 days after study drug discontinuation.
  - f. Laboratory test (hematology and blood chemistry) will be repeated at Baseline/Enrollment to confirm eligibility only if the last test is available > 2 weeks from Baseline/Enrollment.
  - g. At Week 1 or at Week 12, an ECG will be performed before drug intake, and two additional ECGs will be performed 2 and 4 h ( $\pm 15$  min) after study drug intake. The ECG should be recorded before the corresponding PK sample is collected.
  - h. 6MWD in participants of  $\geq 6$  to  $< 18$  years of age able to understand and perform the test correctly.
  - i. Conducted within 14 days before Day 1 (Visit 2).
  - j. Confirmation of iMTD.
  - k. Physical exam only for areas of interest (general appearance, cardiovascular, and respiratory system).
  - l. Complete examination.
  - m. Height required at Screening and Week 16 only.
  - n. Echocardiography should be performed prior to physical exertion (eg, 6MWT).
- 6MWD 6 minute walk distance; 6MWT 6 minute walk test; d day(s); appl. applicable; ECG electrocardiogram; h hour(s); iMTD individual maximum tolerated dose; M month; Mod. modified; NT pro BNP N terminal pro b type natriuretic peptide; NYHA New York Heart Association; PK pharmacokinetic(s); Tel. telephone call; TSH thyroid stimulating hormone; W week; WHO FC World Health Organization functional class.

**Table 5 Visit and assessment schedule after Week 16**

Period	Site visits for participants during the first 12 months following Week 16 (M4)	Site visits for participants after 12 months	Phone calls for participants after 12 months	Unscheduled visit	End-of-Treatment	Safety follow-up Tel.
Name	Visit 9, 10, 11, 12	Visit 13, 14, 15 ...	Tel.	Unscheduled visit	EOT	EOS
Time e	Site visits every 3 months (M7, M10, M13, M16) ± 15 days	Site visits every 6 months (M22, M28, M34...) ± 15 days	Phone call: every 6 months (M19, M25, M31, M37...) alternating with visits ± 15 days	If medically indicated or recommended for assessing PAH progression	Last dose of study drug + up to 7 days	Phone call: 30 days after last dose of study drug + up to 7 days
Previous/Concomitant medications for PAH	X	X		X	X	
Mod. NYHA/WHO FC	X	X		X	X	
Panama FC	X	X		X	X	
PAH signs/symptoms	X	X		X	X	
PAH-related non-pharmacological interventions	If applicable					
Physical examination	X c	X c		X	X c	
Growth: Weight and height	X	X		X	X	
Vital signs (blood pressure, heart rate,)	X	X		X	X	
Echo	X d			X	X	
6MWD test	X b	X		X	X	
Tanner stage	X	X				
Childbearing potential	X	X	X	X	X	
Pregnancy test (if appl.)	X	X	X a	X	X	X
Laboratory test (Hematology/Chemistry)	X	X		X	X	
TSH	X	X		X	X	
Thyroid antibodies	X when medically indicated					
T3 and T4	X when TSH is abnormal or when medically indicated					
Plasma NT pro-BNP	X	X		X	X	
ECG	X	X			X	
Study drug dispensing	X	X		X		
Drug accountability	X	X		X	X	

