### C) Hyperthyroidism

Hyperthyroidism has been observed in 1% of the participants treated with selexipag in the GRIPHON study [Uptravi® USPI, Uptravi® SmPC].

The investigator is asked to inform the participants and the parents and provide guidance that they should be proactive and report if, at any time during study treatment, the participant experiences clinical signs of hyperthyroidism (eg, sudden weight loss even if appetite and the amount and type of food remain the same or even increased), tachycardia, arrhythmia or palpitations, nervousness, anxiety and irritability, tremor, sweating, an enlarged thyroid gland, difficulty sleeping).

If the participant experiences new or worsening of pre-existing hyperthyroidism during the course of treatment with study medication that, in the opinion of the investigator, cannot be adequately controlled with anti-thyroid medications, the study drug must be permanently discontinued and the participant monitored until resolution of this condition.

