## 5.2 Previous and concomitant therapy

The use of all study-concomitant therapy (including contraceptives and traditional and alternative medicines, eg, plant-, animal-, or mineral-based medicines) will be recorded in the eCRF. Previous therapy must be recorded in the eCRF if discontinued less than 42 days prior to the signing of the ICF. The generic name, start/end dates of administration (as well as whether it was ongoing at start of treatment and/or EOS), route, dose, and indication will be recorded in the eCRF.

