### 5.2.2 Allowed concomitant therapy

The PAH-specific therapies allowed as background therapies are ERAs and PDE-5 inhibitors. The dose must have been stable for at least 3 months prior to the first dose of study treatment. For diuretic therapy, the dose must have been stable for at least 1 month prior to the first dose of study treatment.

Single administration of medications used for acute vasodilator testing during RHC procedure is allowed (eg, i.v./inhaled prostacyclin or inhaled nitric oxide or oral sildenafil).

Any change in concomitant therapy or its dose must be recorded in the eCRF.

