### 5.2.3 Forbidden concomitant therapy

Strong and moderate inhibitors of CYP2C8 (eg, gemfibrozil, clopidogrel, deferasirox, teriflunomide) and inhibitors of UGT1A3 and UGT2B7 (valproic acid, probenecid, and fluconazole) are prohibited from 2 weeks prior to enrollment and until the last dose of selexipag + 3 days.

As selexipag and its active metabolite ACT-333679 are IP-receptor agonists, prostacyclin (epoprostenol) and prostacyclin analogs (i.e., treprostinil, iloprost, beraprost except for acute vasodilator testing during RHC procedure) are prohibited from 2 months prior to enrollment until the last dose of selexipag + 3 days or PAH worsening.

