## 7.2 Study assessments

The study assessments are listed in [Table 4](#) and [Table 5](#). The assessments to be performed during each visit are marked with an 'X'.

All study assessments are performed by qualified study personnel (medical, nursing, or specialist technical personnel) and are recorded in the eCRF, unless otherwise specified. Study assessments performed during unscheduled visits will also be recorded in the eCRF. The following order of assessments is recommended: PK samples, safety assessments, efficacy assessments, other assessments (unless otherwise specified in [Table 4](#) and [Table 5](#) and in the assessment descriptions below).

If the principal investigator (PI) delegates any study procedure/assessment for a participant, eg, blood sampling to an external facility, they should inform the Sponsor to whom these tasks are delegated. The set-up and oversight will be agreed upon with the Sponsor. The supervision of any external facilities remains the responsibility of the PI.

Calibration certificates / evidence of equipment maintenance for the below-listed equipment used to perform study assessments must be available prior to the screening of the first participant:

- Body weight scale
- Temperature measurement devices for study treatment storage area and freezer.

Calibration certificates / evidence of equipment maintenance of other equipment should be available as per local requirements.

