- Treatment with Endothelin Receptor Agonist (ERA) monotherapy – identified by the following preferred terms (“Ambrisentan” OR “Bosentan” OR “Sitaxentan” OR “Macitentan”) AND NOT (“Sildenafil” OR “Tadalafil” OR “Vardenafil” OR “Udenafil”) AND NOT “Riociguat”.
- Treatment with phosphodiesterase type 5 (PDE-5) inhibitor monotherapy – identified by the following preferred terms (“Sildenafil” OR “Tadalafil” OR “Vardenafil” OR “Udenafil”) AND NOT (“Ambrisentan” OR “Bosentan” OR “Sitaxentan” OR “Macitentan”) AND NOT “Riociguat”.
- Treatment with combination of both ERAs and PDE-5 inhibitors – identified by the following preferred terms (“Ambrisentan” OR “Bosentan” OR “Sitaxentan” OR “Macitentan”) AND (“Sildenafil” OR “Tadalafil” OR “Vardenafil” OR “Udenafil”) AND NOT “Riociguat”.
- Treatment with prostacyclin/analogs (irrespective of treatment with ERAs or PDE-5 inhibitors or “Riociguat”) – identified by the following preferred terms “Iloprost” OR “Epoprostenol” OR “Treprostinil” OR “Beraprost” (it is expected to be rare as prostacyclin/analogs are not allowed to be co-administered according to the study protocol).

- Treatment with soluble guanylate cyclase stimulator (irrespective of ERAs or PDE-5 inhibitors or prostacyclin/analogs) – identified by the preferred term “Riociguat”.

All medications/therapies will be listed together. A different flag will indicate if the medication is previous or concomitant respectively. Additionally, forbidden and PAH-specific medications will be flagged.

All summaries will be provided by age cohort and body weight group.

All PAH-related non-pharmacological interventions recorded on the dedicated eCRF form will be listed.

If missing end date or the medications ended on or after first dose date of the study drug, the medication will be classified as concomitant medication. If both start date and end date are missing, then this medication will be considered as both previous and concomitant medications.

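### After Week 16, the Protocol's Table 5 schedules only PAH medications for recording, in conflict with Sections 5.2 and 5.2.2, so long-term capture of prohibited inhibitors and other non-PAH drugs may be incomplete or vary by site

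*Protocol*

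**What the plan says.** - **Protocol Table 4 (to Week 16).** The row reads "Previous/Concomitant medications", with no limit by indication. It is marked at Screening, Baseline, Weeks 4, 6, 12 and 16, and at none of the telephone contacts.
- **Protocol Table 5 (after Week 16).** The row becomes "Previous/Concomitant medications for PAH". It is marked at site visits, unscheduled visits and EOT, but not at the six-monthly calls or the EOS call. No footnote explains the narrowing.
- **Protocol 7.2.** The X marks in the two tables define what is done at each visit.
- **Protocol 5.2.** The general rule covers "The use of all study-concomitant therapy (including contraceptives and traditional and alternative medicines", and asks among other things whether each therapy was ongoing at EOS.
- **Protocol 5.2.2.** "Any change in concomitant therapy or its dose must be recorded in the eCRF".
- **Protocol 5.2.3.** CYP2C8, UGT1A3 and UGT2B7 inhibitors "are prohibited from 2 weeks prior to enrollment and until the last dose of selexipag + 3 days".
- **Protocol 7.1.2.** At an unscheduled visit for suspected PAH worsening, the preferred assessments include concomitant medications in general, contraceptives among them.
- **COVID-19 appendix.** A vaccine given to a participant is to be entered in the eCRF as a concomitant medication.
- **SAP 3.3.** All medications taken during study treatment are summarised, PAH-specific or not, and listed. "Additionally, forbidden and PAH-specific medications will be flagged".

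**The concern.** The instruction that a site follows visit by visit is narrower than the general recording rule, and nothing says which prevails. A coordinator working from Table 5 has no prompt to ask about an antifungal, an antiepileptic or a thyroid drug after Week 16. A coordinator working from Section 5.2 would record them all. Both would be following the protocol.

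The stake is the interpretation of long-term safety. Safety and tolerability form the only secondary objective, and the safety endpoints, including TSH and hematology changes, run to EOT + 3 days. The prohibition on metabolic inhibitors lasts as long. If an exposure-raising inhibitor is started in Month 20 and not entered, an adverse event that follows it cannot be explained from the database. A TSH or hemoglobin change cannot be set against a treatment that was never recorded. SAP 3.3 makes no allowance for a collection scope that changes at Week 16, so a missing flag could mean either no use or no entry.

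**Working it through.** The plan gives no figure to reproduce on this point. The check is a comparison of texts, followed by one calculation of how much treatment time is involved.

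**Step 1: scope of the texts that govern recording**

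| Source | Which drugs | When |
|---|---|---|
| Table 4 | All | Marked visits to Week 16 |
| Table 5 | For PAH only | Site visits, unscheduled visits, EOT |
| Section 5.2 | All | No time limit; status at EOS requested |
| Section 5.2.2 | Any change | No time limit |
| Section 7.1.2 | All | Unscheduled visits for suspected worsening |
| COVID-19 appendix | Vaccines (not for PAH) | No time limit |

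Table 5 is the only one of these that restricts by indication. It conflicts with Sections 5.2 and 5.2.2 throughout the period after Week 16, with Section 7.1.2 in its own unscheduled-visit column, and with Section 5.2 again at EOS, where the row has no mark.

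**Step 2: do the prohibited drugs fall inside the narrowed row?** Section 5.2.3 names gemfibrozil, clopidogrel, deferasirox, teriflunomide, valproic acid, probenecid and fluconazole. None is among the PAH-specific preferred terms in SAP 3.3, and none would ordinarily be called a medication for PAH. The Table 5 row therefore prompts no check for them, although the prohibition runs through the whole period.

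**Step 3: telephone contacts.** Table 4 marks no medication check at any call. The blank at the Table 5 calls is therefore not a narrowing relative to Table 4. Adverse events are marked at the Table 5 calls and at EOS.

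**Step 4: share of treatment time under the narrowed row.** With T the total treatment time in weeks,

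share = (T − 16) / T.

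A Table 5 month is 28 days, so Month 16 is 64 weeks. Years are converted as 365.25/7 weeks.

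| Assumed T | Calculation | Share |
|---|---|---|
| 32 weeks | 16 / 32 | 50.0% |
| 52 weeks | 36 / 52 | 69.2% |
| 64 weeks (Month 16) | 48 / 64 | 75.0% |
| 2 years (104.4 weeks) | 88.4 / 104.4 | 84.7% |
| 5 years (260.9 weeks) | 244.9 / 260.9 | 93.9% |
| 7 years (365.2 weeks) | 349.2 / 365.2 | 95.6% |

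The upper rows come from Protocol 3.1.1 (treatment up to 5 years after the last participant's first visit) and the synopsis (study duration of about 7 years). No expected mean duration is stated, so only a range can be given. These are shares of calendar time under the narrowed row, not estimates of the proportion of data missing.

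**Step 5: what does not depend on this row**
- The primary PK endpoint is determined within the 12-week up-titration period, which Table 4 covers.
- The hyperthyroidism discontinuation criterion (Protocol 5.1.10 C) applies when, in the investigator's opinion, the condition "cannot be adequately controlled with anti-thyroid medications". It does not turn on an eCRF medication entry.
- The clinical-worsening endpoint is built from the disease-progression and clinical-worsening records (SAP 5.2.5), not from the medication log.

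**The case against.** The strongest reply is that nothing is switched off. Sections 5.2 and 5.2.2 still require full recording after Week 16, Section 7.1.2 and the COVID-19 appendix presuppose it, and SAP 3.3 refers to general medication pages in the eCRF. On this view Table 5 only schedules a prompt, and data are lost only where a site follows the row label and overlooks two explicit rules. There are partial back-ups: use of a prohibited drug is a protocol deviation to be documented (Protocol 12.5), major deviations are listed (SAP 3.4), TSH testing continues, and adverse events are collected at every contact. SAP 3.3 also plans no medication table by study period and no adjustment of laboratory changes for medication, so no specified analysis fails.

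Much of this stands. A reader might infer from Table 5 that non-PAH drugs go unrecorded after Week 16. The documents do not support that, because Sections 5.2 and 5.2.2 say the opposite and the eCRF build is not described. A reader might also infer that the hyperthyroidism stopping rule fails, or that i.v. diuretics drop out of the clinical-worsening endpoint. Neither follows, for the reasons in Step 5 of the working. An i.v. diuretic given for PAH worsening also fits the Table 5 label on a plain reading.

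The reply does not remove the conflict. Section 7.2 gives the tables operative force, no text ranks the two instructions, and the deviation route works only if someone first learns of the drug.

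**Conclusion.** The conflict is real and worth correcting. The supported conclusion is that capture of non-PAH medication after Week 16 may be incomplete or may differ between sites, and that an absence of forbidden-medication flags in that period cannot be taken as evidence of no use. The cost falls on the interpretation of long-term safety listings and summaries. The primary PK result is untouched.

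The period affected is more than half of treatment time for anyone treated beyond 32 weeks. How much is actually missing cannot be derived from the documents. It depends on how the eCRF pages are built and on which instruction each site followed.

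**What to change.** 1. Reconcile the passages by making the Table 5 row an unrestricted concomitant-medication row, as in Table 4 and Section 5.2.
2. Mark the row at EOS, where Section 5.2 asks for ongoing status. Adding it to the six-monthly calls is optional and is not needed to match Table 4.
3. Query sites for non-PAH medications not yet entered for participants past Week 16, taking prohibited inhibitors first and then drugs that affect TSH or hemoglobin.
4. State in the SAP or the CSR any period in which only PAH medications were captured, so that the forbidden-medication flags are read accordingly.

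The cost is one table row in an amendment or site communication, plus some retrospective data entry across about 30 planned sites. No visit, procedure or blood sample is added, and no clinical rule changes.
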